5. OBJECTIVE, SUMMARY, AND RATIONALE OF THE PROPOSED RESEARCH

The primary objective of the study is to assess the correlation between BIA-derived body composition parameters (e.g., fat mass, fat-free mass, total body water, phase angle) and eGFR in hemodialysis patients.

The study will investigate how BIA and eGFR can be used together to more effectively monitor nutritional interventions in hemodialysis patients. The study will also assess the prevalence of malnutrition and protein-energy wasting (PEW) in the study population using BIA and eGFR data.

Hemodialysis patients often suffer from complex nutritional problems due to the interplay between kidney function, protein-energy wasting, and fluid management. Current nutritional assessments in hemodialysis patients are limited, with most relying on clinical observations or basic biochemical tests. A more comprehensive, non-invasive approach is needed to assess both nutritional status and fluid balance. The study will determine whether comparing BIA metrics with eGFR provides a better picture of the patient's nutritional and kidney health, which could improve patient outcomes and dialysis management.

Malnutrition, fluid balance disorders, and protein-energy wasting (PEW) are common in hemodialysis patients due to the effects of chronic kidney disease (CKD) and dialysis therapy. Nutritional status is a critical factor influencing patient outcomes but is often under-monitored.

Traditional methods of assessing kidney function, such as estimated glomerular filtration rate (eGFR), provide an overview of kidney health but do not directly measure body composition or nutritional value. In contrast, bioelectrical impedance analysis (BIA) provides detailed information on body composition, including fat mass, fat-free mass, total body water, and phase angle. The aim

of this study is to investigate the relationship between BIA-derived nutritional markers and eGFR to assess their combined utility in evaluating the nutritional status of hemodialysis patients.

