7. INCLUSION AND EXCLUSION CRITERIA

Sample size: 25-30 adult hemodialysis patients will be recruited.

Inclusion criteria:

- Patients must be 18 years or older.
- Patients must have been receiving regular hemodialysis for at least the last 6 months.

Exclusion criteria:

- Patients with a pacemaker or implanted defibrillator will not be included, as these are contraindications for BIA.
- Pregnant women will not be included due to changes in body composition and safety concerns.
- Patients who have recently had an acute illness or surgery that affected their hydration or nutritional status, as this could provide inaccurate body composition results.

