8. RESEARCH METHODOLOGY DESCRIPTION

Study type: Observational, cross-sectional study

Data collection:

Patient data will be collected from the hemodialysis department of Tartu University Hospital. All participating patients will undergo BIA. BIA analysis will be performed using dialysis-related measurement instruments, as described in the methodology section. This will be done before routine dialysis and does not require a separate visit. The patient does not need to come in specifically for this purpose.

The following data will be collected from participating patients:

Demographic data:

- Age
- Gender
- Height
- Weight
- Body mass index (BMI)
- Duration of dialysis (months/years)

Bioelectrical impedance analysis (BIA):

- Fat mass
- Fat-free mass

- Total body water
- Extracellular water
- Phase angle

Laboratory parameters:

- eGFR

Bioelectrical impedance measures body fat, muscle, and water using a low-voltage electric current that is harmless and imperceptible to the patient. Two electrodes are placed on the wrist and two on the ankle, similar to an EKG but faster (approximately 5 minutes). Although the procedure is safe, it requires minimal patient preparation. Measurements will only be taken from patients who consent. Measurements include fat mass, fat-free mass, total body water, extracellular water, and phase angle. To minimize fluid shifts, measurements will be taken before dialysis. eGFR will be taken from the patient's recent blood test. eGFR data will be collected routinely and will use measurements from the last 6 months. Clinical data such as dialysis duration and comorbidities will also be considered.

Data analysis will be performed using statistical software (SPSS).

The analysis will include several steps to thoroughly evaluate the relationship between bioelectrical impedance analysis (BIA) parameters and estimated glomerular filtration rate (eGFR) in hemodialysis patients. Descriptive statistics will summarize the main characteristics, such as age, gender, dialysis duration, eGFR, and BIA parameters. Pearson or Spearman correlation tests will be used to assess relationships between BIA measurements (e.g., fat mass, lean body mass, phase angle) and eGFR. Multivariate regression analysis will identify significant predictors of malnutrition and clinical outcomes, focusing on factors such as phase angle, lean body mass, and fluid status.

Data will be collected from the hemodialysis department of Tartu University Hospital.

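### One sentence in Section 5 promises a better picture of kidney health, but a correlation of BIA with on-dialysis eGFR cannot by itself support a conclusion on kidney function

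*Protocol*

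**What the plan says.** Protocol Section 5 sets the primary objective: "The primary objective of the study is to assess the correlation between BIA-derived body composition parameters" and eGFR in hemodialysis patients. It gives eGFR a role without any caveat for dialysis: "Traditional methods of assessing kidney function, such as estimated glomerular filtration rate (eGFR), provide an overview of kidney health". One rationale sentence then goes further: "The study will determine whether comparing BIA metrics with eGFR provides a better picture of the patient's nutritional and kidney health". The closing aim of the same section is narrower and speaks only of "combined utility in evaluating the nutritional status of hemodialysis patients".

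Three other places fix what the eGFR value is:

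- Section 7, inclusion: "Patients must have been receiving regular hemodialysis for at least the last 6 months".
- Section 8, source and window of eGFR: "eGFR will be taken from the patient's recent blood test", and "eGFR data will be collected routinely and will use measurements from the last 6 months".
- Section 8, in the description of the BIA procedure: "To minimize fluid shifts, measurements will be taken before dialysis". No such timing is given for the blood sample behind eGFR.

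eGFR is the only laboratory parameter on the Section 8 list. Section 3 says that BIA is the only test added for the study, so no measure of residual kidney function is planned. The protocol names no marker or equation for its own eGFR; the one equation mentioned, in Section 11, belongs to a cited study.

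**The concern.** In a patient on regular dialysis, the blood value behind eGFR depends on dialysis removal and on the time since the last session, as well as on what the patient's own kidneys still do. If eGFR is creatinine-based, it also depends on muscle mass, which BIA measures on the other side of the same correlation, and on the age and sex terms of the equation. This is general reasoning, and the creatinine basis is an assumption.

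A positive, null or negative correlation can then arise for reasons unrelated to kidney function. As Section 5 is worded, such a result could be reported as evidence on kidney health. Section 9 promises openness about limitations in general, but the protocol nowhere states this one.

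**Working it through.** **Step 1: is every eGFR an on-dialysis value?** Time on hemodialysis at entry is at least 6 months (Section 7). The eGFR look-back is at most 6 months (Section 8). Counted back from the same date, the second window lies inside the first, so every eligible eGFR is drawn on dialysis. Neither window has a stated anchor date, but data collection lasts only February to March 2025 (Section 6), so any mismatch is small.

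**Step 2: how large could the artefact be?** The protocol gives no figure to reproduce. What follows is illustrative and every input is assumed.

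Inputs: n=28 (within the planned 25-30); 3000 simulated studies per setting; 60% men; age 62 (SD 14); height 1.75 (0.07) m in men and 1.62 (0.065) m in women; fat-free mass (FFM) index 18.5 (2.0) in men and 15.5 (1.8) in women. Assumed equation: eGFR = 142 × (Cr/k)^-1.2 × 0.9938^age × 1.012 if female, with k = 0.9 in men and 0.7 in women.

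No kidney-body link: creatinine generation is proportional to FFM and clearance to FFM^a, so Cr = 8 × (FFM/50)^(1-a) × lognormal scatter. Mean Spearman r of eGFR with FFM:

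| Clearance scaling | scatter 0.15 | 0.25 | 0.35 | 0.50 |
|---|---|---|---|---|
| a=0 (same for all) | -0.52 | -0.38 | -0.29 | -0.22 |
| a=0.5 | -0.07 | -0.05 | -0.04 | -0.03 |
| a=1 (proportional to FFM) | +0.44 | +0.31 | +0.23 | +0.17 |

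At a=0 larger patients have higher creatinine, hence lower eGFR. At a=1 creatinine is unrelated to FFM, and the positive r comes from the sex term: at equal creatinine and age, male eGFR is (0.9/0.7)^1.2 / 1.012 = 1.34 times female, and men have more FFM.

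**Step 3: does a real link show?** Let clearance = (1 - share) × (FFM/50)^a + share × residual function, with residual function lognormal (log SD 0.8). It is either independent of FFM or linked to it (mean Spearman 0.47). At share 20% and scatter 0.25:

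| Scaling | no link | real link |
|---|---|---|
| a=0 | -0.34 | -0.16 |
| a=1 | +0.17 | +0.37 |

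Within a row the real link raises r by about 0.2. Between rows the unknown scaling moves r by about 0.5 (from -0.34 to +0.17, or from -0.16 to +0.37).

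**Step 4: draw timing.** A session that lowers creatinine by 60% (assumed) multiplies eGFR by (1/0.4)^1.2 = 3.0. In a single-pool model with no link and scatter 0.15, mean r is:

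| Dialysis amount | pre only | post only | half and half |
|---|---|---|---|
| Same for all | -0.18 | -0.76 | -0.24 |
| Proportional to body water | +0.44 | +0.44 | +0.22 |

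Confining the analysis to one timing class moves r further from zero in three of these four cases, and it also reduces n.

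**The case against.** The strongest reply is that the disputed words are one phrase of rationale. The primary objective is only to assess a correlation, the closing aim and the study title concern nutritional status, and the Section 8 regression targets malnutrition and clinical outcomes. Nothing in Section 8 plans an inference on kidney function. All of this stands, and it limits the point to the sentence and to what is recorded about eGFR.

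Three stronger readings are tempting and are not supported.

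- A reader might infer that eGFR carries no information here, or that the primary correlation is invalid. It can be computed, and eGFR keeps some information on residual function.
- A reader might take the remark on disease progression in Section 11 as this study's own claim. It draws a lesson from a cited study of CKD stages 3-5 and does not say how this correlation will be read.
- A reader might infer that a real link would typically look weaker than no link, by setting +0.17 (no link) against -0.16 (real link). Those two values come from different clearance scalings. At the same scaling the real link gives the higher r.

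It is also fair that marker, equation and adjusted analyses may be settled in a statistical analysis plan, and that blood draws may in practice all be taken at the same point. Silence on those details is not the fault. The objective's wording, however, belongs to the protocol, and the current wording claims more than the listed data can give.

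**Conclusion.** The point holds in a limited form. The statement that the study will determine something about kidney health describes a property the design lacks, because every eGFR is an on-dialysis value, no residual-function measure is listed and the draw is untimed. That part follows from the text of Sections 3, 5, 7 and 8.

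The size is illustrative. With no true link, mean r for fat-free mass spans about -0.5 to +0.4 under the assumed creatinine equation, population and scaling. For comparison, two-sided p<0.05 needs |r| of about 0.40 at n=25 and 0.36 at n=30, so an artefact alone could reach significance. Fat mass and phase angle were not simulated. Since nothing in the protocol fixes the scaling, neither the sign nor the size of r can be read as kidney function. The primary correlation and the nutritional-status aim stand.

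**What to change.** **Section 5.** Replace the kidney-health sentence, for example with: *The study will describe the association between BIA measures and a routine eGFR index obtained on dialysis, as part of assessing nutritional status. This correlation will not by itself be taken as evidence on kidney function.*

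**Section 8.** For each eGFR, take the marker, the equation and the timing of the draw relative to dialysis from the existing records, and report them descriptively. Add the age- and sex-adjusted eGFR-BIA correlation with a 95% interval as a descriptive sensitivity analysis; age and gender are already collected. It can show confounding by those two factors but cannot identify every source at n=25-30. In the no-link simulations the single-study 95% ranges of the adjusted r overlap: -0.65 to +0.06 (a=0, scatter 0.35), -0.59 to +0.15 (a=0.5, scatter 0.25) and about -0.39 to +0.40 (a=1).

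Do not restrict the primary correlation to one timing class; as the timing table shows, this can enlarge the artefact, and it costs patients.

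**Cost.** A more modest claim, three extra record fields, and an update of the Section 8 data list and of the description given to patients and the ethics committee. No new test, visit or patient is needed.

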3. RESEARCH FUNDING

The only research to be conducted specifically for this study is the BIA analysis. This will be carried out by the researcher using equipment belonging to the University of Tartu (UT), for which no additional fee will be charged. The equipment used includes a bioelectrical impedance analysis device, which is already available and in use in the nephrology department. All other reviewed tests are those that have already been performed for clinical reasons and registered in the patients' hospital records in the eHL system.

The study (comparative analysis of bioelectrical impedance analysis (BIA) and estimated glomerular filtration rate (eGFR) for assessing nutritional status in hemodialysis patients) does not have an external funding source. This study will be conducted in compliance with ethical research standards. All aspects of the study, including data collection, analysis, and reporting, will be carried out without external financial support.

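### Section 5 promises to determine whether BIA with eGFR gives a better picture of nutrition, but the study collects no independent nutritional criterion or designated comparator to judge it by

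*Protocol*

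**What the plan says.** Protocol Section 5 contains several aims of different strength.

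- The declared primary aim is descriptive: "The primary objective of the study is to assess the correlation between BIA-derived body composition parameters" and eGFR.
- A comparative claim follows: "The study will determine whether comparing BIA metrics with eGFR provides a better picture" of nutrition and kidney health. The section closes by saying that the relationship is studied "to assess their combined utility in evaluating the nutritional status of hemodialysis patients".
- Existing practice is described as limited, "with most relying on clinical observations or basic biochemical tests".
- The study will also "assess the prevalence of malnutrition and protein-energy wasting (PEW) in the study population using BIA and eGFR data".

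Section 8 lists the data: age, gender, height, weight, BMI and dialysis duration; five BIA measures; and eGFR as the only laboratory parameter. Clinical data, with dialysis duration and comorbidities as examples, are also to be considered.

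Section 8 plans descriptive statistics, then correlations ("Pearson or Spearman correlation tests will be used to assess relationships between BIA measurements" and eGFR), then a multivariate regression for predictors of malnutrition and of clinical outcomes. The regression focuses on factors such as phase angle, lean body mass and fluid status.

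**The concern.** To call one assessment better than another takes a comparator and a yardstick independent of both. Section 5 names what is used now, but Section 8 collects neither clinical nutritional observations nor routine biochemistry as a comparator, and it lists no independent measure of nutrition.

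Without a yardstick, either result can be read in favour of joint use. A strong BIA-eGFR correlation can be presented as mutual confirmation, although it may mean redundancy. A weak one can be presented as complementarity, although it may mean that eGFR says little about nutrition in these patients. Section 4 already describes the two tools as complementary, so the favourable reading is ready to hand. At stake is a statement of combined utility in the report that the data did not test.

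**Working it through.** The plan gives no figure on this point to reproduce. The 25-30 patients in Section 7 are stated without derivation and play no part in the argument. The check sets the aims against the data, then shows what each planned analysis can deliver.

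**1. Aims against data**

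| Needed to judge joint use | In the Section 8 data list? |
|---|---|
| Nutritional criterion independent of BIA and eGFR | None named; BMI is there only as demographic data |
| Current assessment as comparator | None designated; eGFR is the only laboratory value |
| Clinical outcome | None named; the design is cross-sectional |

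**2. What the correlation can show**

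Let B be a BIA parameter, E be eGFR and Y a nutritional criterion, which the study does not measure. With both predictors,

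R² = (r_BY² + r_EY² − 2·r_BY·r_EY·r_BE) / (1 − r_BE²).

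The gain from adding eGFR to BIA is R² − r_BY². The study estimates r_BE only. All values below are assumed for illustration, with r_BY = 0.5, so BIA alone gives 0.25.

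For r_BE = 0.3 the denominator is 1 − 0.09 = 0.91:

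- r_EY = 0.15: (0.25 + 0.0225 − 0.045)/0.91 = 0.250; gain 0.000
- r_EY = 0.30: (0.25 + 0.09 − 0.09)/0.91 = 0.275; gain 0.025
- r_EY = 0.50: (0.25 + 0.25 − 0.15)/0.91 = 0.385; gain 0.135

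The gain at other values of r_BE:

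| r_BE | r_EY = 0 | 0.15 | 0.30 | 0.50 |
|---|---|---|---|---|
| 0 | 0.000 | 0.023 | 0.090 | 0.250 |
| 0.3 | 0.025 | 0.000 | 0.025 | 0.135 |
| 0.6 | 0.141 | 0.035 | 0.000 | 0.062 |

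Every row runs from no gain to a material one. Knowing r_BE exactly would not say where in the row the truth lies.

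**3. What the regression can show**

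- Its first outcome, malnutrition, is to be assessed from BIA and eGFR (Section 5). The predictors in focus, phase angle, lean body mass and fluid status, correspond to the BIA measurements. To the extent that the classification uses those measurements, the model returns its own definition.
- Its second outcome, clinical outcomes, has no variable in the data list.
- eGFR is not among the predictors named. Even if it were added, a gain in predicting a classification built partly from eGFR would be no independent evidence.

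**The case against.** **The primary objective is sound.** It is the BIA-eGFR correlation, which the listed data and tests address. The disputed sentence sits in the rationale of a small, unfunded cross-sectional study. This stands, and it limits the point to overclaiming in the wording around the primary aim. Even so, the sentence says what the study will determine, and the combined-utility aim is stated as an aim.

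**The plan goes beyond correlation.** A reader might infer that only correlations are planned. Section 8 does not support that, because it also plans a multivariate regression. The objection is right on the fact, but the regression does not rescue the aim, for the reasons given in the working.

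**The data list is partly open.** A reader might infer that no conceivable result could bear on the question. That is too strong: BMI is collected and could serve as a crude indicator, and the clinical data are given by example. What the protocol supports is narrower: no criterion or comparator is designated, and no planned analysis answers the question.

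**Model detail belongs in an analysis plan.** Whether models with and without eGFR are compared may fairly be left there. An analysis plan cannot, however, supply a criterion that was never collected.

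**Sample size is not the cause.** A reader might blame the 25-30 patients. Imprecision is a separate matter, and a larger study with the same data list would have the same gap.

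**Conclusion.** The point holds as a mismatch between the stated aims and the collected data. Section 5 promises a judgement on whether joint use is better and on combined utility. Section 8 collects no independent nutritional criterion and designates no comparator, and malnutrition is assessed from the two measures under study. Neither the correlations nor the regression can show that joint use is better.

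Under the assumed BIA-criterion correlation of 0.5, an observed BIA-eGFR correlation of 0.3 is compatible with a gain in R-squared of 0.000 to 0.135. The range is 0.000 to 0.250 at a BIA-eGFR correlation of 0, and 0.000 to 0.141 at 0.6, for eGFR-criterion correlations between 0 and 0.50. These ranges are illustrative; the conclusion rests on the missing criterion, not on the particular values.

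The point does not invalidate the study or its primary correlation objective. It limits what the report may conclude, and the wording should be changed.

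**What to change.** Reword Section 5 along these lines: *The study describes the association between BIA parameters and eGFR in hemodialysis patients; it is not designed to determine whether their joint use is better for assessing nutritional status.* Replace the combined-utility aim to match, and draw no such conclusion in the report. The cost is one or two sentences and a more modest stated aim. No new data are needed.

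If the sponsor wants to keep the question, it must first add a nutritional criterion that is independent of BIA and eGFR and already in the hospital record. Section 3 says of the non-BIA data that "All other reviewed tests are those that have already been performed for clinical reasons", so extraction fits the existing approach. That a suitable criterion is on record is an assumption, since Section 8 names only eGFR. Serum albumin is an awkward choice: it would itself belong to the basic biochemistry that Section 5 wants to improve on.

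The analysis should then compare BIA alone (one prespecified parameter) with BIA plus eGFR by an optimism-corrected measure, such as adjusted or cross-validated R-squared, labelled exploratory. A raw in-sample change in R-squared would not do, because in nested least-squares models it cannot be negative. With no true relation its expected value is about 1/(n − 1): 1/24 = 0.042 at n = 25 and 1/29 = 0.034 at n = 30.

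This option costs one more variable, possible missing values, coverage of that variable in the ethics submission and one more analysis. It would show only whether eGFR adds to BIA. A claim against current practice would also need current practice recorded as a comparator.

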6. RESEARCH TIMELINE

Data collection: February – March 2025

Data analysis: April 2025

Report writing, completion, and presentation: April – June 2025

7. INCLUSION AND EXCLUSION CRITERIA

Sample size: 25-30 adult hemodialysis patients will be recruited.

Inclusion criteria:

- Patients must be 18 years or older.
- Patients must have been receiving regular hemodialysis for at least the last 6 months.

Exclusion criteria:

- Patients with a pacemaker or implanted defibrillator will not be included, as these are contraindications for BIA.
- Pregnant women will not be included due to changes in body composition and safety concerns.
- Patients who have recently had an acute illness or surgery that affected their hydration or nutritional status, as this could provide inaccurate body composition results.

